Nocturia	Waking at night one or more times to void (i.e. any voiding associated with sleep disturbance between the time the subject goes to bed with the intention to sleep until the time the subject gets up in the morning with the intention to stay awake).
Overactive Bladder	Urgency, with or without urgency incontinence, usually with frequency and nocturia, which can be described as the OAB syndrome, urge syndrome or urgency-frequency syndrome.
Randomization	The process of assigning trial subjects to treatment or control groups using an element of chance to determine assignments in order to reduce bias.
Run-In Failure	Screened subject who did not fulfill protocol inclusion and/or exclusion criteria at Visit 2. Subjects who are considered a run-in failure cannot be re-screened into the study at a later date.
Screened	A subject who has signed informed consent and has performed the screening visit.
Screening Failure	Screened subject who did not fulfill protocol inclusion and/or exclusion criteria, or decided not to participate anymore (withdrew consent) prior to Visit 2. Subjects who are considered a screen failure at Visit 1 due to an acute condition that resolved (e.g., a treated UTI, an ECG that a cardiologist cleared, discontinuation of a prohibited or restricted medication) may be re-screened into the study at a later date.

Terms	Definition of terms
Serious Adverse Event	An adverse event is considered “serious” if, in the view of either the Investigator or Sponsor, it results in any of the following outcomes: results in death, is life threatening, results in persistent or significant disability/incapacity or substantial disruption of the ability to conduct normal life functions, results in congenital anomaly, or birth defect, requires inpatient hospitalization or leads to prolongation of hospitalization, or a medically important event.
Stress urinary incontinence	The complaint of involuntary leakage on effort or exertion, or on sneezing or coughing.
Subject Number	Number assigned to each subject by the Interactive Response System after signature of informed consent and prior to any specific procedures.
Treatment-Emergent Adverse Event	An adverse event starting or worsening in the period from first double-blind medication intake until 30 days after last double-blind medication intake.
Urgency	A sudden and compelling desire to pass urine that is difficult to defer.

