Dose Titration ^k			X			
Instruct Subject on 3-day Diary ^l	X	X	X	X		
Subject Completes 3-day Diary including HBPM		X ^m	X ^m	X ^m	X ^m	
EQ-5D-5L		X	X	X	X	

Table continued on next page

	Screening/ Tamsulosin Hydrochloride Run- In	Treatment Period				Follow-up Phone Call
		1	2	3	4	
Visit	1	2	3	4	5	6
Day	-28	1	28	56	84	114
Week	-4	0	4	8	12	16
Visit Windows	+/- 3 d	—	+/- 7 d	+/- 7 d	+/- 7 d	+/- 3 d
Visit Windows (Study Days) ^a	-31 to -25	—	21 to 35	49 to 63	77 to 91	111-117
OAB-q		X	X	X	X	
PPBC		X	X	X	X	
PPIUS		X	X	X	X	
TS-VAS		X	X	X	X	
Review Subject Diary ⁿ		X	X	X	X	

- a. After Visit 1 (Screening/tamsulosin hydrochloride run-in), visit windows/study days will be calculated based on the Visit 2 (Baseline) visit date. Study procedures (e.g., bladder scan) for a particular visit do not need to be completed on the visit date if this is not feasible for the subject, as long as study procedures are performed per protocol within the applicable visit window. Any procedure not done or performed outside the applicable visit window will be noted as a protocol excursion.
- b. Subjects must take at least 22 days, but no more than 34 days of tamsulosin hydrochloride run-in medication.
- c. Reminder Phone Call to complete the diary and to answer any questions is to occur approximately 7 days prior to the visit.
- d. Randomization is to occur after confirming all eligibility criteria and after performing all other visit procedures at Visit 2.
- e. Blood samples need not be fasting. A central laboratory will be used for all laboratory hematology and biochemistry/PSA assessments. Local laboratories will be used for all urinalysis and urine culture and sensitivity.
- f. Urine culture and sensitivity must be performed for positive leukocyte esterase (LCE), nitrites, or turbidity, or at the discretion of the PI. It is not required to send isolated trace positive leukocyte esterase samples for culture. If a subject has a UTI (defined as > 100,000 CFU), the subject may be rescreened after successful treatment of the UTI (confirmed by a laboratory result of negative urine culture).

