5.4.3 Adverse Events

Adverse Event collection will begin from the time of informed consent and continue through the Follow-up Phone Call (Visit 6). See Section 5.5 Adverse Events and Other Safety Aspects for information regarding adverse event collection and data handling.

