5.4.9 Follow-up Phone Call to Patients

Subjects will be contacted 4 weeks after Week 12/End of Treatment (Visit 5) by telephone for a Follow-up Phone Call (Visit 6) to assess concomitant medications and any adverse events that may have occurred following the end of treatment.

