5.5.6 Follow-up of Adverse Events

All AEs occurring during or after the subject has discontinued the study are to be followed up until resolved or judged to be no longer clinically significant, or until they become chronic to the extent that they can be fully characterized.

If during AE follow-up, the adverse event progresses to an "SAE", or if a subject experiences a new SAE, the Investigator must immediately report the information to the Sponsor.

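### The 30-day TEAE window does not match the end of adverse event collection at the Visit 6 call, whose timing the text and Table 1 give differently

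*Protocol*

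**What the plan says.** The Definition of Key Study Terms lets a TEAE start or worsen from the first double-blind dose "until 30 days after last double-blind medication intake".

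Section 5.4.3 sets when events are collected: "Adverse Event collection will begin from the time of informed consent and continue through the Follow-up Phone Call (Visit 6"). Footnote j of Table 1 repeats this. Table 1 schedules no contact after Visit 6.

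The timing of Visit 6 is given in two ways:

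- **Text.** Section 5.4.9 says "Subjects will be contacted 4 weeks after Week 12/End of Treatment (Visit 5) by telephone", in order to ask about "any adverse events that may have occurred following the end of treatment". The synopsis and Section 2.2.1 give the same 4 weeks.
- **Table 1.** Visit 5 is at Week 12, Day 84, with a window of Day 77 to 91. Visit 6 is at Week 16, Day 114, with a window of Day 111 to 117. Under footnote a, "visit windows/study days will be calculated based on the Visit 2 (Baseline) visit date", so the Visit 6 window stays fixed when Visit 5 is early or late.

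The synopsis (Duration of Treatment) caps double-blind treatment at 12 weeks, and Section 5.1.1 describes 4 weeks plus the remaining 8. Neither says on which day the last dose is taken when Visit 5 is early or late.

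**The concern.** The TEAE definition promises 30 days of observation after the last dose. The last scheduled adverse event contact is timed from Visit 5 in one place and from Visit 2 in another, and neither rule is tied to the last dose. A man who keeps every permitted window can therefore have his last contact before his TEAE window closes, while another is followed past it.

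Safety and tolerability are the secondary objective (Section 2.1). TEAE incidence is the first listed safety variable (Section 2.3.4) and is reported as numbers and percentages (Section 7.5.1). An event that is not collected counts as no event, and the analysis cannot recover it. At stake are some under-counting of late TEAEs and percentages that mix different lengths of observation.

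**Working it through.** **Inputs.** TEAE window: 30 days after last dose (Definition of Key Study Terms). Visit 5: nominal Day 84, permitted Days 77 to 91, so 15 days. Visit 6: nominal Day 114, permitted Days 111 to 117, so 7 days (Table 1). Text rule: Visit 5 plus 28 days (Section 5.4.9). Permitted day pairs: 15 × 7 = 105. A call on day 30 or later is taken to cover the window.

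**1. Nominal schedule.** 114 − 84 = 30 days, exactly the TEAE window. The week row gives Week 16 − Week 12 = 4 weeks = 28 days, so Table 1 differs from itself by 2 days.

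**2. Text rule.** With the last dose on the day of Visit 5, the call comes at day 28, which is 30 − 28 = 2 days short.

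**3. Do the two rules agree?** Visit 5 + 28 must lie in 111 to 117, so Visit 5 must lie in 83 to 89. That is 7 of the 15 permitted days. On the other 8 (Days 77 to 82, 90 and 91), a call exactly 4 weeks after Visit 5 is outside the Table 1 window, which footnote a treats as a protocol excursion.

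**4. Table 1 rule, last dose to call.** Interval = Visit 6 day − last dose day. Because the protocol does not fix the day of last dose, three assumptions are shown.

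| Last dose taken on | Shortest interval | Largest shortfall | Pairs under 30 days |
|---|---|---|---|
| Visit 5, but not after Day 84 (12-week cap read literally, first dose Day 1) | 111 − 84 = 27 | 3 days | 27 of 105 |
| The day before Visit 5 | 111 − 90 = 21 | 9 days | 42 of 105 |
| The day of Visit 5, up to Day 91 | 111 − 91 = 20 | 10 days | 49 of 105 |

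Count for the first row: Visit 5 on Days 77 to 81 gives no short pairs. Days 82, 83 and 84 give 1, 2 and 3. Each of Days 85 to 91 gives 3. The total is 1 + 2 + 3 + 7 × 3 = 27.

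Count for the last row: Days 82 to 87 give 1 + 2 + 3 + 4 + 5 + 6 = 21. Days 88 to 91 give 7 each, or 28. The total is 49.

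Under the last assumption, the whole Visit 6 window covers the 30 days only if Visit 5 is on Day 81 or earlier (111 − 81 = 30). With Visit 5 on Day 88 or later, no permitted call does (117 − 88 = 29). The longest permitted interval is 117 − 77 = 40 days.

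**The case against.** The strongest reply is that the schedule was built to fit: the nominal days give exactly 30, and only visit tolerances and a loose 4 weeks open a gap. That is right about the origin. The tolerances are still permitted, and the text rule falls 2 days short even on target if the last dose is on the day of Visit 5.

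Second, the 10-day figure needs dosing to continue to Day 91, which sits badly with the 12-week cap. It also needs a call 20 days after Visit 5, which fits Table 1 only by breaching the 4-week text. Both points stand. The 10 days is an upper bound, and under the cap the bound is 3 days.

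Third, the gap is a small part of the whole TEAE window. Counting from Day 1, it is 3 of 84 + 30 = 114 days (3%) or 10 of 91 + 30 = 121 days (8%), all off drug. Criteria for hypertension and tachycardia that use office readings are largely untouched, since no office visit follows Visit 5. This lowers the weight of the point but does not remove it, because other events are still collected by the call.

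Three stronger readings are tempting and are not supported:

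- A reader might infer from 49 of 105 (47%) that about half the men are affected. The figure counts permitted day pairs with equal weight, and the protocol gives no distribution of visit dates.
- A reader might infer that the missing days go wholly unobserved. Section 5.5.6 says "All AEs occurring during or after the subject has discontinued the study are to be followed up until resolved" and asks for prompt reporting of new SAEs during that follow-up, so unscheduled reports may catch some events. What is missing is a scheduled contact.
- A reader might infer bias in the treatment comparison. The same windows apply to both blinded, randomised arms, and nothing in the protocol suggests that call timing differs by arm.

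**Conclusion.** The inconsistency is real, and its severity is minor. The TEAE definition, the 4-week text and the Table 1 window cannot all be met for every man who keeps to his permitted visit days. The shortfall from last dose to call is at most 3 days if dosing stops by Day 84, and at most 10 days if it continues to a Visit 5 on Day 91. The protocol does not settle which applies. Many permitted day pairs have no shortfall at all.

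The consequence is some under-counting of late TEAEs and unequal observation length in both arms alike. The conflict between the two call-timing rules rests on none of the last-dose assumptions: it arises on 8 of the 15 permitted Visit 5 days.

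**What to change.** Reconcile the TEAE definition, Table 1 (week row, day row, window and footnote a), Section 5.4.9, Section 2.2.1 and the synopsis, in one of two ways:

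- Tie Visit 6, in both the text and Table 1, to the actual last double-blind dose, with its earliest permitted day not before the TEAE window ends. The shortfall is then zero on every permitted Visit 5 day.
- Restate the TEAE window so that it ends no later than the shortest follow-up the schedule guarantees. On the present Table 1 that is 27 days if dosing stops by Day 84, or 20 days if it can run to Day 91.

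The first option moves the same phone call a few days later for some men and adds no visit. The second changes only wording, but shortens the TEAE window by 3 to 10 days. Either way, the protocol should make clear how the day of last dose relates to an early or late Visit 5, because the size of the gap depends on it.

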1 INTRODUCTION

1.1 Background

Overactive bladder (OAB) syndrome is a highly prevalent medical condition. The prevalence of OAB is estimated to be 34 million in the US and 22 million in Europe [Irwin et al, 2009; Kim et al, 2006; Stewart et al, 2003; Milsom et al, 2001]. International Continence Society (ICS) defines OAB as urgency, with or without urge incontinence, usually with frequency and nocturia [Abrams et al, 2003; Lee and Lee, 2014]. Prevalence of OAB symptoms increases with age, and the prevalence of OAB wet (with incontinence) is greater in women than in men [Jaffe and Te, 2005]. In clinical practice, it is recognized that men may experience OAB symptoms concurrent with those of benign prostatic hyperplasia (BPH).

BPH is a condition affecting over 50% of men by age 60 [Bechis et al, 2014]. It is also a common cause of lower urinary tract symptoms (LUTS) such as frequent urination, urgency, nocturia, and the sensation of incomplete bladder emptying [Miller and Tarter, 2009]. In 2008, an estimated 917 million men worldwide were affected by LUTS from BPH [Irwin et al, 2011]. LUTS can be divided into storage and voiding symptoms, with BPH predominantly associated with voiding LUTS symptoms. Patients with voiding symptoms may also have concomitant storage symptoms. Analysis of the general population identified that the combination of storage and voiding LUTS was the most common type of LUTS, affecting 8.9% of the general population sample in a multinational, population-based study (EPIC) [Irwin et al, 2009; Irwin et al, 2006].

Alpha-blockers, such as tamsulosin hydrochloride, are commonly prescribed to manage BPH symptoms but may fail to alleviate storage (OAB) symptoms [Lee and Lee, 2014]. Thus, the American Urological Association (AUA) has identified combination therapy with an α -blocker and anticholinergic as a potential treatment option for patients with BPH and coexisting OAB symptoms [AUA Guidelines, 2010].

The use of antimuscarinics (e.g., tolterodine and solifenancin) as add-on therapy to alpha-blockers such as tamsulosin hydrochloride has been evaluated in a number of clinical studies in men with OAB and BPH [ADAM study by Chapple et al, 2009; VICTOR study by Kaplan et al, 2009; TIME study by Kaplan et al, 2006]. Evaluated add-on therapies were generally found to be well-tolerated and showed an added benefit over alpha-blocker monotherapy in improving OAB-related symptoms.

Mirabegron (Myrbetriq®/Betmiga®) is a potent and selective human beta-3 adrenergic receptor agonist approved for the treatment of OAB with symptoms of urge, urinary incontinence, urgency and urinary frequency [Mirabegron US Package Insert, 2015 and Myrbetriq Canadian Monograph, March 2015, EU SmPC, 2015]. For the mirabegron monotherapy clinical development program, 32 phase 1 studies and 13 phase 2 and 3 studies (10 in patients with OAB, 1 in patients with LUTS/bladder outlet obstruction (BOO) and 2 in patients with type 2 diabetes mellitus) were conducted. Several global phase 3 studies have demonstrated the efficacy, safety and tolerability of once daily mirabegron in patients with OAB. In these clinical trials, the incidence of urinary retention did not increase with

mirabegron, and it was lower than that of placebo and the active control antimuscarinic [Nitti et al, 2013]. In a phase 2 study of 200 men with LUTS and BOO, mirabegron was also found to be safe and generally well-tolerated, with no adverse effects on either the detrusor pressure at maximum flow rate or on the maximum flow rate [Study 178-CL-060].

The use of the beta-3 adrenergic agonist mirabegron to treat OAB symptoms as add-on therapy to tamsulosin hydrochloride will be evaluated for efficacy, safety, and tolerability of the combination therapy. It is anticipated from previous studies of add-on therapies, the combination of mirabegron and tamsulosin hydrochloride will show an added benefit over α -blocker monotherapy in improving OAB-related symptoms.

1.2 Summary of Non-clinical and Clinical Data

Detailed information on the non-clinical studies conducted with mirabegron and tamsulosin hydrochloride can be found in the approved product labeling, Summary of Product Characteristics (SmPC) and US Package Insert for mirabegron and tamsulosin hydrochloride, copies of which will be made available to the Investigator, Institutional Review Boards [IRB], Independent Ethics Committees [IEC] and other bodies as appropriate. Summaries of findings from non-clinical and clinical studies with mirabegron and tamsulosin hydrochloride which may have relevance for the current study are listed below.

1.2.1 Mirabegron (YM178)

Mirabegron was approved for the treatment of OAB in adults in Japan in 2011 and in the US, Canada and Europe in 2012. Mirabegron is a selective human beta-3 adrenergic agonist and the first of a new class of compounds with a different mode of action from the current standard of care, muscarinic receptor antagonists, in the treatment of patients with OAB. Antimuscarinics and mirabegron both reduce micturition frequency and incontinence. Data from the phase 2 study 178-CL-100 showed that mirabegron has a similar effect size to antimuscarinics. Consistent with the Phase 2 data, one phase 3b comparative trial (178-EC-001) between mirabegron and solifenacin in patients dissatisfied with their previous antimuscarinic showed that the two drugs had similar effect sizes for micturition frequency and incontinence.

1.2.1.1 Summary of Non-clinical Studies of Mirabegron

Mirabegron is a potent and selective agonist of the human beta-3 adrenergic receptor. Mirabegron has low intrinsic activity for human beta-1 and beta-2 adrenergic receptors. Mirabegron has no significant affinity for other pharmacological targets in a comprehensive test battery of receptors, ion channels and enzymes. Mirabegron directly relaxes human bladder in vitro through activation of beta-3 adrenergic receptors. Studies in conscious and anesthetized rat models of bladder function demonstrate modulation consistent with a beneficial profile in OAB patients.

Increases in heart rate have been observed following mirabegron administration to rats, dogs, and monkeys. Decreases in blood pressure were observed in dogs but not in rats or monkeys. Assessment of the potential for mirabegron to delay cardiac repolarization demonstrated that mirabegron and its most abundant human metabolites were free from effects on cardiac

repolarization in isolated dog Purkinje fibers and guinea pig papillary muscles. Furthermore, in isolated perfused dog ventricular tissue neither mirabegron nor its metabolites induced electrophysiological changes. Mirabegron and its five most abundant human metabolites did not significantly alter the IKr (hERG), IKs (hKvLOT1/mink), Ito (hKv4.3/KChip2.2), Ina (hNAV1.5), or Ica (hCav 1.2) conductance in in vitro studies at relevant concentrations (>100-fold human C_{max}) at a 100 mg dose.

Single and repeat dose toxicology studies in dogs, monkeys, and rats demonstrate cardiovascular changes at high doses. In a 13-week rat toxicology study, significant increases in plasma alanine aminotransferase (ALT) were observed at doses of 30 mg/kg and higher (22-fold higher than maximum recommended human dose). Modest (less than 2-fold) increases in alkaline phosphatase (ALP) and aspartate aminotransferase (AST) were observed at high doses (72-fold higher than the maximum recommended human dose), together with reversible changes in hepatocytes. Modest elevation of ALT was also observed in monkeys but the changes observed were deemed to be below the level of toxicological significance and there were no changes in liver histopathology. There were no significant changes in liver enzymes or liver histopathology in dogs. Mirabegron was not genotoxic, carcinogenic, or teratogenic in the battery of conventional in vitro and in vivo studies.

1.2.1.2 Summary of the Pharmacokinetics of Mirabegron

After oral administration of mirabegron in healthy volunteers, peak mirabegron plasma concentrations were attained between 3 to 5 hours. The absolute bioavailability increases from 29% at a dose of 25 mg to 45% at a dose of 150 mg under fasted conditions in healthy volunteers. Mean C_{max} and AUC_{inf} increased more than dose proportionality over the recommended dose range. Steady state concentrations were achieved within 7 days of once daily dosing with mirabegron. The C_{max} and AUC_{tau} of mirabegron and its metabolites following multiple oral doses in older adult subjects (≥ 65 years) were similar in those in younger subjects (18 to 45 years). The C_{max} and AUC_{tau} of mirabegron were approximately 40-60% higher in females than in males. The mean terminal $t_{1/2}$ is comparable in both sexes. Evaluation of special populations in the phase 1 studies demonstrated that volunteers with severe renal impairment (CrCL 15 to 29 mL/min or eGFR 15 to 29 mL/min per $1.73 m^2$) or moderate hepatic impairment (Child-Pugh Class B) had an approximately 2-fold increase in exposure to mirabegron relative to normal healthy volunteers.

The in vitro oxidative metabolism of mirabegron in human liver microsomes is primarily mediated by cytochrome P450 (CYP) 3A4, but a possible role for CYP2D6 could not be excluded. In vitro CYP inhibition studies suggest that mirabegron is a moderate and time-dependent inhibitor of CYP2D6 and a weak inhibitor of CYP3A4.

1.2.1.3 Summary of Clinical Data with Mirabegron

The clinical development program consists of 48 completed clinical studies to date over approximately 10 years and is comprised of 13,640 subjects (1,909 volunteers and 11,731 patients) including patients with OAB, type 2 diabetes mellitus, and lower urinary tract symptoms (LUTS)/bladder outlet obstruction (BOO). A total of 34 phase 1 studies and

14 phase 2 and 3 studies (11 in patients with OAB, 1 in patients with LUTS/BOO and 2 in patients with type 2 diabetes mellitus) have been conducted globally.

Mirabegron has been studied across the dose range of 25 mg to 200 mg once daily in OAB patients. Mirabegron 25 mg, 50 mg, and 100 mg demonstrated statistical superiority compared to placebo for the co-primary endpoints of incontinence episodes and micturition frequency. Both the 50 mg and 100 mg doses also demonstrated superiority compared to placebo for almost all key secondary endpoints defined in the phase 3 program.

Evaluation of the combined safety data from the mirabegron clinical program to date shows mirabegron to be safe and well tolerated. The incidence of Treatment Emergent Adverse Events (TEAEs) in the active treatment group is comparable with the incidence in the placebo group. The most frequently reported TEAE was hypertension which includes reports of blood pressure above the normal range, and BP increased from baseline, occurring predominantly in subjects with baseline hypertension. Most commonly reported adverse reactions (>2% and >placebo) were hypertension, nasopharyngitis, urinary tract infection and headache. Most of the events were mild or moderate in intensity. Other adverse reactions occurring at greater than 1% and greater than placebo include constipation, upper respiratory infection, arthralgia, diarrhea, tachycardia, abdominal pain and fatigue (Table 2). The number of serious TEAEs is low and comparable across mirabegron and placebo treatment groups.

Table 2 Percentage of Patients with Adverse Reactions, Derived from All Adverse Events, Exceeding Placebo Rate and Reported by 1% or More Patients Treated With MYRBETRIQ® 25 mg or 50 mg Once Daily

	Placebo (%)	MYRBETRIQ® 25 mg (%)	MYRBETRIQ® 50 mg (%)
Number of Patients	1380	432	1375
Hypertension*	7.6	11.3	7.5
Nasopharyngitis	2.5	3.5	3.9
Urinary Tract Infection	1.8	4.2	2.9
Headache	3	2.1	3.2
Constipation	1.4	1.6	1.6
Upper Respiratory Tract Infection	1.7	2.1	1.5
Arthralgia	1.1	1.6	1.3
Diarrhea	1.3	1.2	1.5
Tachycardia	0.6	1.6	1.2
Abdominal Pain	0.7	1.4	0.6
Fatigue	1	1.4	1.2

* Includes reports of blood pressure above the normal range, and BP increased from baseline, occurring predominantly in subjects with baseline hypertension.

In the US Package Insert, mirabegron is contraindicated in patients with hypersensitivity reactions. It has warnings and precautions for increases in blood pressure, angioedema, urinary retention in patients with bladder outlet obstruction, and in patients taking drugs metabolized by CYP2D6.

In the Canadian Monograph, mirabegron is contraindicated in patients with severe uncontrolled hypertension, patients who are pregnant, and patients who are hypersensitive to mirabegron or to any ingredient in the formulation or component of the container. Mirabegron has warnings and precautions for neoplasm, Stevens-Johnson syndrome, increases in serum ALT/AST and bilirubin, QTc prolongation, increases in blood pressure and heart rate, urinary retention, and in patients taking drugs metabolized by CYP2D6. The monograph does not recommend use of mirabegron in patients with severe hepatic impairment, end stage renal disease, pregnant and nursing women, and pediatric patients (<18 years of age).

In the EU Summary of Product Characteristics (EU SmPC), mirabegron is contraindicated in patients with hypersensitivity reactions and for those with uncontrolled hypertension (SBP > 180, or DBP > 110). It has warnings and precautions for increases in blood pressure, QTc prolongation, and urinary retention in patients with bladder outlet obstruction. It recommends not to use in patients with moderate or severe hepatic impairment (Child-Pugh Class B or C) or end stage renal disease.

For further information, please refer to the full prescribing information for mirabegron [Mirabegron US Package Insert, 2015 and Myrbetriq Canadian Monograph, March 2015, EU SmPC, 2015].

